**D. Description, Risks and Justification of Procedures and Data Collection Tools:**

The panel will be performed all on positive pediatric blood cultures that are positive during laboratory working hours. The panel results will be released to clinical providers. This is necessary in order to assess the clinical impact and clinical decision-making based on the results. A local investigator will review all positives throughout the day and inform the treatment team of the results. All enrolled patients will undergo chart review to assess for clinical outcomes, such as antimicrobial agents, ICU days, hospital days, and mortality. We will need to collect this information in order to assess the clinical impact of this panel. The information will be stored directly into RedCap database which will be accessible only to key study personnel. The study involves minimal risk to the patient, as it only includes risk of loss of confidentiality. We are requesting a full waiver of informed consent, as subjects will be assigned to the intervention versus control group based on the timing of positive cultures. Patients, providers and investigators will not have control over which patients will be placed into the control or intervention groups, as this will be randomized based on time of positivity. This reflects the reality of laboratory capabilities in low-middle income countries, such as Guatemala.

**E. Potential Scientific Problems:** There will be challenges of working in Guatemala City, as this is a limited-resource setting. The culture around antibiotic usage is different than in the U.S. and therefore may impact the expected reduction in time to effective and optimal antimicrobial therapy. Currently they only obtain a single blood culture bottle during collection, but this is standard in many low-middle income countries.

**F. Data Analysis Plan:** Hospital Roosevelt has 800 pediatric blood cultures processed monthly (with about 5% positivity). Based on preliminary data, only 37% of patients with positive blood cultures received optimal therapy based on predefined consensus guidelines. Of those who receive optimal therapy, the median time to therapy is 90 hours. With the addition of a blood culture identification panel, we expect to see a reduction in time to optimal antimicrobial therapy to 30 hours. This estimate is based on U.S. data conducted at our institution showing a reduction to 27 hours on average with BCID plus antimicrobial stewardship.

Target Enrollment: 100 patients over 4 month study period

**G. Summarize Knowledge to be Gained:** This study is important to evaluate the impact that rapid multiplex blood culture identification PCR panels have on improving clinical outcomes in low-middle income countries such as Guatemala. It has shown significant impact in reduction in time to optimal antimicrobial therapy in high-income countries. In countries such as Guatemala, with higher rates of antimicrobial resistance and broad-spectrum antimicrobial usage, the potential impact is greater and could lead to a mortality benefit. If a significant clinical impact is observed, we would advocate for continued use of the panel at Hospital Roosevelt, as well as 24/7 implementation if a significant difference is seen between the intervention and prospective control group. This could be translatable to other low-middle income countries.

Rapid Blood Culture Identification Panel in Pediatric Patients in Guatemala

NCT05314816

Statistical Analysis Plan

v. 2/23/2023

Statistical Analysis Plan

Objective: to evaluate the clinical impact of the BioFire BCID2 panel in children with bacteremia in Guatemala.

Study Design: Pragmatic clinical trial comparing intervention to two different control groups. Intervention and concurrent control group allocated by time of blood culture positivity. Also comparing to historical controls.

Primary outcome: time to optimal antimicrobial therapy

Secondary outcomes:

- Time to effective antimicrobial therapy
- Time to pathogen identification
- Mortality
- Length of hospital stay
- Antibiotic days of therapy (DOT)
- Number of unique antibiotics
- Total ICU days

Definitions to consider:

Patient Group

Intervention= patient was enrolled in the intervention group and received the BCID2 intervention within 12h timeframe

Concurrent control= patient was enrolled in the study and did not receive the BCID2 intervention within 12h from blood culture positivity

- Weekday controls= Patient with positive blood culture from 1pm-11:59pm Mon-Thurs
- Weekend controls= Patient with positive blood culture from 1pm Fri- 11:59pm Sunday

Per protocol =patient received intervention based on original allocation.

- Per protocol intervention= Patient allocated to intervention based on timing of blood culture AND BCID2 was performed within 8h timeframe.
- Per protocol control= Patient allocated to control group based on timing of blood culture AND no BCID2 was performed.

Protocol deviation=Patient intended to remain in the allocated group, but there was an unintentional deviation from protocol.

- Protocol deviation intervention= BCID2 run between 8-12h in patient allocated to intervention.
- Protocol deviation control= BCID2 was sent clinically >12h from positive culture in patient allocated to control group OR patient originally allocated to intervention group but BCID2 was not performed.

Sub-groups

On-panel true pathogens= Pathogens on the BCID2 panel that are always considered real pathogens per protocol. These include, *E. faecalis*, *E. faecium*, *Listeria*, *Staph aureus*, *Strep pneumonia*, *Strep agalactiae*, *Strep pyogenes*, *Acinetobacter baumannii*, *B. fragilis*, *Enterobacterales*, *Enterobacter cloacae*, *E. coli*, *Klebsiella aerogenes*, *Klebsiella oxytoca*, *Klebsiella pneumoniae*, *Proteus*, *Salmonella*, *Serratia matcescens*, *Haemophilus influenza*, *Neisseria meningitidis*, *Pseudomonas aeruginosa*, *Stenotrophomonas maltophilia*, *Cryptococcus*, *Candida species*.

Gram negative on-panel pathogen= On-panel true pathogens as above that are Gram negatives only. These include *Acinetobacter baumannii*, *B. fragilis*, *Enterobacterales*, *Enterobacter cloacae*, *E. coli*, *Klebsiella aerogenes*, *Klebsiella oxytoca*, *Klebsiella pneumoniae*, *Proteus*, *Salmonella*, *Serratia matcescens*, *Haemophilus influenza*, *Neisseria meningitidis*, *Pseudomonas aeruginosa*, *Stenotrophomonas maltophilia*.

Gram negative pathogen= On or off-panel pathogens that are Gram negatives.

On-panel classic contaminant= Gram positive pathogens on the BCID2 panel that are often considered contaminants (note, may be considered real in the analysis). These include, *Staph epi*, *Staph lugdunensis*, *other Staph species*, *other Strep species*.

Off-panel non-Gram negatives (other)= typically contaminants.

True pathogens (on and off panel)= excluding common contaminants.

Polymicrobial= More than one organism was detected by BCID2 and/or Vitek.

Primary outcomes

Optimal antibiotic=typically narrowest spectrum agent based on predefined consensus guidelines

Effective antibiotic= any antibiotic susceptible based on susceptibilities even if overly broad.

Time to optimal antimicrobial therapy=time blood culture received in lab to time of first dose of “optimal” antibiotic. Censor at 14 days. Censor for death if “never reached” optimal. Stoppage of antibiotics if deemed a contaminant.

Time to effective antimicrobial therapy= time of blood culture received in lab to time of first dose of “effective” antibiotic. Censor at 14 days. Censor for death if “never reached” effective. Stoppage of antibiotics if deemed a contaminant.

Clinician discretion (Intention to treat analysis (ITT))=effective and optimal therapy determined based on whether **treating physicians** considered the pathogen real or a contaminant. Optimal therapy allowed additional antibiotics if the treating team was also treating for other syndromic diagnoses, such as culture-negative sepsis (if pathogen detected deemed to be a contaminant), nosocomial pneumonia, etc. if called out in diagnoses. Definitions created for optimal therapy for nosocomial pneumonia, culture-negative sepsis, etc.

- Time to effective therapy in ITT:
 - Time from blood culture received in lab (time 0) to effective therapy
 - Time from blood culture positivity (time 0) to effective therapy
- Time to optimal therapy in ITT:
 - Time from blood culture received in lab (time 0) to effective therapy
 - Time from blood culture positivity (time 0) to effective therapy

Pathogen directed (Per protocol analysis) =effective and optimal therapy based on **strict definitions** for real pathogen or contaminant created by study team. Strict optimal antibiotic definitions without allowing for additional antibiotics for culture-negative sepsis or nosocomial pneumonia, etc. Does allow for additional antibiotics for clear other indications (pyelonephritis, CAP, dacrocystitis, intra-abdominal abscess, etc.) or another organism isolated (excluding urine and trach cultures). Not allowing for more controversial diagnoses such as sepsis or nosocomial pneumonia.

- Time to effective therapy in per protocol:
 - Time from blood culture received in lab (time 0) to effective therapy
 - Time from blood culture positivity (time 0) to effective therapy
- Time to optimal therapy in per protocol:
 - Time from blood culture received in lab (time 0) to effective therapy
 - Time from blood culture positivity (time 0) to effective therapy

Secondary outcomes

Time to pathogen identification= Time from time of blood culture receipt in lab (time 0) to identification of a pathogen. For control patients, this is the time to Vitek. For intervention patients, this is the time to BCID2 if the BCID2 was positive for an on-panel pathogen or time to vitek if the BCID2 was negative.

- Control: time to Vitek
- Intervention:
 - If BCID2 positive → calculate time to BCID2 result
 - If BCID2 negative → calculate time to Vitek

Total antibiotic days=all days that patient was on antibiotics (any dose of antibiotic) from date that blood culture was drawn. Capped at 14 days or date of death.

Antibiotic days of therapy =Sum of antibiotics each day over 14-day period. For example if 2 antibiotics were each given over 5 days, this would count as 10 DOT.

Number of different antibiotics=Number of unique antibiotics given over the 14-day period.

Length of stay=date admitted to date patient left the study (date of death/discharge or lapse of 30 days). Censor at 30 days.

Total ICU days=date admitted in ICU to date transferred out or date of death/discharge. Censor at 30 days.

Time to death= Time from blood culture obtained to time of death.

Number of deaths within 24h of blood culture draw= Use time of death calculation above to determine the number of patients who died <24h

Overview of Analyses to perform:

- All interventions vs. all concurrent controls (including protocol deviations) vs. historical controls
 - Demographics
 - All outcomes (primary and all secondary endpoints)
 - Sensitivity analysis comparing weekday vs. weekend controls
- Per protocol controls vs. per protocol intervention (excluding protocol deviations)
 - Demographics
 - All outcomes (primary and all secondary endpoints)
- Clinician discretion (ITT) analysis (controls vs. interventions)

- Number of contaminants vs. true pathogens
- Time to optimal therapy
- Time to effective therapy
- Pathogen directed (Per protocol) analysis (controls vs. interventions)
 - Number of contaminants vs. true pathogens
 - Time to optimal therapy
 - Time to effective therapy
- Gram negatives only (on- and off- panel)
 - Demographics
 - Time to optimal therapy
 - Time to effective therapy
 - Mortality
- On-panel true pathogens only
 - Demographics
 - Time to optimal therapy
 - Time to effective therapy
 - Mortality
- On-panel Gram negatives only
 - Demographics
 - Time to optimal therapy
 - Time to effective therapy
 - Mortality
- True pathogens (on and off panel)
 - Demographics
 - Time to optimal therapy
 - Time to effective therapy
 - Mortality

Figure 1: CONSORT Diagram

Table 1: Patient Characteristics

*Wilcoxon test of medians

**chi-square test

Table 1A: Supplemental table with demographics from sub-groups.

	Per protocol Intervention	Per protocol Control	p-value	True on-panel pathogen Intervention	True on-panel Pathogen controls	p-value	All Gram negative (GN) Interv.	All GN control	p-value	All GN weekDAY controls	p-value (compare to GN interv.)	On-panel GN Interv.	On-panel GN control	p-value
--	---------------------------	----------------------	---------	-------------------------------------	---------------------------------	---------	--------------------------------	----------------	---------	-------------------------	---------------------------------	---------------------	---------------------	---------

Age in months (median, IQR)*														
Categorical age groups (0-30 days, 1- 5.99mo, 6-11.99mo, 12month- 23.99month, 24 month-4.99y, >=5y)**														
Female (n, %)**														
No antecedent medical conditions (N, %)**														
Immunocompromised (N, %)**														
Central line (N, %)**														
Required ICU stay (N, %)**														

Table 2: Organisms isolated in culture (Vitek)

ORGANISM	INTERVENTION N=135 (%)*	CONCURRENT CONTROL N=219 (%)*	STUDY TOTAL N=354 (%)*	HISTORICAL CONTROLS N=99 (%)*	Weekend controls N=XX (%)	Weekday controls N=XX (%)
BCID2 Panel organisms						
Acinetobacter calcoacetius-baumannii complex (n, %)						
Bacteroides fragilis						
Haemophilus influenzae						
Neisseria meningitidis						
Pseudomonas aeruginosa						
Stenotrophomonas maltophilia						

Enterobacter cloacae complex						
Escherichia coli						
Klebsiella aerogenes						
Klebsiella oxytoca						
Klebsiella pneumoniae group						
Proteus spp.						
Salmonella spp.						
Serratia marcescens						
Enterococcus faecalis						
Enterococcus faecium						
Listeria monocytogenes						
Staphylococcus aureus						
Staphylococcus epidermidis						
Staphylococcus lugdunensis						
Streptococcus agalactiae (Group B)						
Streptococcus pneumoniae						
Streptococcus pyogenes (Group A)						
Candida albicans						
Candida auris						
Candida glabrata						
Candida krusei						
Candida parapsilosis						
Candida tropicalis						
Cryptococcus neoformans/gattii						

Other coagulase-negative Staphylococcus species						
Other Streptococcus species						
Total on-panel targets						
Non-BCID2 organisms						
Bacillus species						
Achromobacter species						
Burkholderia species						
Shewanella species						
Sphingomonas species						
Other Acinetobacter species						
Pantoea species						
Other Pseudomonas species						
Alloioicoccus species						
Aeromonas species						
Leuconostoc species						
Kocuria species						
Citrobacter freundii						
Gram positive Bacillus (no ID)						
Moraxella species						
Pandoraea species						
Kluyvera species						
Total non-BCID2 targets						

*n= number of cultures. Some cultures grew more than one isolate. Percentage of each organism was calculated from the total number of cultures.

Table 2A: Supplemental table of organisms for sub-groups. (Will likely add historical controls to supplemental table)

ORGANISM	Per protocol Intervention N=112 (%)*	Per protocol controls N=192 (%)*	Protocol deviation interventions N=23 (%)*	Protocol deviation controls N=27(%)*
BCID2 Panel organisms				
Acinetobacter calcoacetius-baumannii complex				
Bacteroides fragilis				
Haemophilus influenzae				
Neisseria meningitidis				
Pseudomonas aeruginosa				
Stenotrophomonas maltophilia				
Enterobacter cloacae complex				
Escherichia coli				
Klebsiella aerogenes				
Klebsiella oxytoca				
Klebsiella pneumoniae group				
Proteus spp.				
Salmonella spp.				
Serratia marcescens				
Enterococcus faecalis				
Enterococcus faecium				
Listeria monocytogenes				
Staphylococcus aureus				
Staphylococcus epidermidis				
Staphylococcus lugdunensis				

Streptococcus agalactiae (Group B)				
Streptococcus pneumoniae				
Streptococcus pyogenes (Group A)				
Candida albicans				
Candida auris				
Candida glabrata				
Candida krusei				
Candida parapsilosis				
Candida tropicalis				
Cryptococcus neoformans/gattii				
Other coagulase-negative Staphylococcus species				
Other Streptococcus species				
Total on-panel targets				
Non-BCID2 organisms				
Bacillus species				
Achromobacter species				
Burkholderia species				
Shewanella species				
Sphingomonas species				
Other Acinetobacter species				
Pantoea species				
Other Pseudomonas species				
Alloioococcus species				
Aeromonas species				
Leuconostoc species				

Kocuria species				
Citrobacter freundii				
Gram positive Bacillus (no ID)				
Moraxella species				
Pandoraea species				
Kluyvera species				
Total non-BCID2 targets				

Table 3: Outcomes

Table 3A: For NICU kids only

	Interventions N=135	Concurrent Controls N=219	p-value	Weekend control	p-value	Weekday control	p-value	Historical controls N=99	p-value
--	------------------------	---------------------------------	---------	--------------------	---------	--------------------	---------	--------------------------------	---------

Table 3B: For non-NICU patients only

Table 3C: Table of outcomes with sub-groups for all units

	Per protocol interventions	Per protocol Controls	p-value	All Gram negative interventions	All Gram negative controls	p-value	All GN weekDAY controls	p-value (compare to GN interv.)	True on-panel pathogens interventions	True on-panel pathogens controls	p-value	On-panel Gram neg interv	On-panel Gram neg control	p-value
--	----------------------------	-----------------------	---------	---------------------------------	----------------------------	---------	-------------------------	---------------------------------	---------------------------------------	----------------------------------	---------	--------------------------	---------------------------	---------

Median total antibiotic days (XX days)													
Median antibiotics DOT													
Number of unique antibiotics in 14-day period													

Table 4: BCID2/Vitek discrepancies in intervention patients

	Number of patients (N, %)
BCID2/Vitek agreed	
BCID2/Vitek disagreed	
BCID2 positive, Vitek negative	
BCID2 negative, Vitek positive	
Species misidentification	
Resistance gene did not match susceptibility	
Organism not on panel	

Other parameters:

- Look at distribution (median with IQR) of time between BCID2 result and team notification (only for intervention patients).
- Look at distribution (median with IQR) of time between BCID2 execution and team notification (only for intervention patients).
- Age distribution and gender between those excluded via initial screening and those included (initially enrolled).

Figures: Kaplan Meier curves for time to optimal and time to effective therapy (using both intention to treat AND per protocol analyses)

1st way- time of blood culture draw as time 0

2nd way- time of blood culture positivity as time 0

Figure 1: Compare interventions vs. concurrent controls vs. Historical controls (all pathogens)

Figure 1A: time to effective therapy ITT

Figure 1B: time to effective therapy per protocol

Figure 1C: time to optimal therapy ITT

Figure 1D: time to optimal therapy per protocol

Figure 1E: time to death (deaths only)

Figure 2: Compare interventions vs. concurrent controls vs. Historical controls (Gram negative rods on-panel and off-panel)

Figure 3: Compare interventions vs. concurrent controls vs. Historical controls (True on-panel pathogens only)

Figure 4: Compare interventions vs. concurrent controls vs. Historical controls (on-panel Gram negative pathogens only)

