##### **C. Study Design and Research Methods**

- a. Currently the standard of care at Hospital Roosevelt is to perform standard blood culture on all specimens that are positive on the automated VIRTUO system. This occurs by trained lab technicians 24/7. Once there is colony growth on the plates via standard culture, the isolate is placed on the VITEK system for identification and susceptibility. This process has been analyzed in the program evaluation and will serve as historical controls.
- b. In this prospective study, we will implement the BioFire FilmArray blood culture identification panel (BCID2), which laboratory technicians will run simultaneously with standard culture after it flags positive on VIRTUO system. We will only run the BCID2 panel on those specimens that become positive during **normal working hours Monday-Friday from 7am to 1pm** due to the inability to staff the laboratory overnight and on weekends. **Those specimens that become positive from 12am to 7am will be run at 7am, as the panel can be run up to 24 hours from positivity per BioFire protocol.** Those that become positive in the evening from 1pm-11:59pm Monday-Thursday will not be run on the BCID2 and will serve as controls. All positive cultures (in both groups) will be plated on agar plates to confirm growth on culture and undergo susceptibility testing per standard current protocols.
- c. Physicians will be notified of panel results, as well as standard culture results per current laboratory protocol, which includes uploading results onto a webpage accessible to all physicians on their mobile device. **BCID2 results will additionally be reported to providers directly by telephone notification or in person by the study PI.** Standard culture results on control patients will be reported per standard protocol of webpage notification.
- d. Antimicrobial stewardship will be continued per current standard of care at Hospital Roosevelt. The Pediatric Infectious Disease fellows and attendings at Hospital Roosevelt review all positive cultures in the microbiology laboratory each morning,

and review results in person with the inpatient teams. **During this study, the local PI will serve as the antimicrobial steward and provide BCID2 results to physicians within 1 hour of notification. We will provide guideline-based recommendations for all BCID2 results to help standardize the stewardship process.**

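### Groups are set by clock time: add a covariate-adjusted analysis of time to optimal therapy, and reconcile the concurrent-control windows in the protocol and SAP

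*SAP*

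**What the plan says.** **Allocation.** SAP, Study Design: "Intervention and concurrent control group allocated by time of blood culture positivity". Protocol section IV.D describes the same rule as randomised, but no chance mechanism is described.

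**Control windows.** Protocol section IV.C.b says that cultures turning positive "in the evening from 1pm-11:59pm Monday-Thursday will not be run on the BCID2 and will serve as controls". It gives Friday 1pm to the end of Sunday to no group. The SAP, under Patient Group, lists a second type of concurrent control: "Weekend controls= Patient with positive blood culture from 1pm Fri- 11:59pm Sunday".

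**Grouping for analysis.** The SAP defines both groups by whether the BCID2 was received within 12 h. A patient allocated to intervention whose panel was not run is counted as a protocol-deviation control.

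**Methods.** The readable SAP names Wilcoxon and chi-square tests as footnotes to Table 1 (patient characteristics) and Kaplan-Meier curves for time to optimal and effective therapy. For time to optimal therapy it specifies "Censor at 14 days. Censor for death if" the optimal regimen was never reached. No regression, covariate set or weighting is named. The bodies of Tables 1 and 3 could not be read in the text available, so this statement covers the readable text only.

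**Existing safeguard.** SAP, Overview of Analyses: "Sensitivity analysis comparing weekday vs. weekend controls". A table header near Table 3A, carrying the whole-study group sizes, has separate p-value columns for weekend and weekday controls.

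**Use of the result.** Protocol section IV.G would advocate "24/7 implementation if a significant difference is seen between the intervention and prospective control group".

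**The concern.** When the clock decides the group, comparability has to be argued or adjusted for. Children whose cultures turn positive at different hours or days may differ in age, unit, underlying disease or line use. An unadjusted contrast would credit any such difference to the panel. The contrast matters because the protocol ties a recommendation for round-the-clock use to its significance.

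The control windows add a second problem. If the SAP's definition is used, more than half of the control time comes from a period that the protocol never designated as control time. Whether weekend care differs is not settled by the documents. Protocol section IV.C.a says of standard culture work, "This occurs by trained lab technicians 24/7", while section IV.C.b restricts the panel's hours "due to the inability to staff the laboratory overnight and on weekends". The planned sensitivity analysis, as worded, sets one control subset against the other and does not re-estimate the panel effect.

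**Working it through.** **1. The SAP's own counts (Tables 2 and 2A).** Intervention 112 + 23 = 135. Concurrent control 192 + 27 = 219. Total 354. These agree.

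**2. Weekly hours per window.**
- Intervention: midnight to 1pm, Monday to Friday: 13 × 5 = 65 h. This reads the overnight rule as Monday to Friday, as the SAP's weekend window implies.
- Weekday control: 11 × 4 = 44 h.
- Weekend control: 11 + 24 + 24 = 59 h.
- Total: 168 h. The protocol leaves 59/168 = 35% of the week without a group.

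**3. Which windows do the group sizes fit?** Assume positivity is uniform over the week.
- Protocol windows: expected intervention share 65/(65 + 44) = 59.6%.
- SAP windows: 65/168 = 38.7%.
- Observed: 135/354 = 38.1% (95% CI 33.1-43.4%). Exact binomial p = 0.87 against the SAP windows and p < 0.001 against the protocol's.
- If all 27 deviation controls had been allocated to intervention, the share would be 162/354 = 45.8%. That still rejects the protocol windows (p < 0.001), but it also lies above 38.7% (p = 0.007). So the close match to the SAP windows depends on few of the 27 having arisen in intervention hours; the mismatch with the protocol does not.

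**4. Weekend share of controls.** 59/(44 + 59) = 57.3%, so 219 × 0.573 ≈ 125 weekend and 94 weekday. Among the 192 per-protocol controls it is about 110 and 82. If the overnight rule ran seven days a week, the windows would be 79, 44 and 45 h, and the share 45/89 = 51%, about 111 of 219. All are approximate, for the reason in step 3.

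**5. Size of a case-mix bias.** The inputs here are assumptions, not figures from the documents: no panel effect; a baseline factor that halves the rate of reaching optimal therapy; 37% (the historical figure) or 80% reaching it by 14 days.
- Approximate unadjusted hazard ratio = (1 − 0.5 × p_int)/(1 − 0.5 × p_ctl).
- 40% versus 50%: 0.80/0.75 = 1.07. 30% versus 50%: 0.85/0.75 = 1.13.
- Simulation (135 versus 219, exponential times, 5,000 runs): 1.07 with 6.9% (37% events) or 8.7% (80% events) false positives; 1.14 with 11.8% or 19.5%.
- With the factor in the model: hazard ratio 1.00 and 4.9-5.3%. This shows only that a measured factor can be removed, since the model was given the one factor simulated.

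**6. What adjustment cannot do.** No allocated control window overlaps the intervention window. In simulation, when clock time itself carries a hazard ratio of 1.3, false positives are 30% unadjusted and 32% adjusted.

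**7. Why the control set matters.** If weekend controls reach optimal therapy at 0.8 or 1.2 times the weekday rate (assumption), the pooled null hazard ratio is 1/(0.427 + 0.573 × 0.8) = 1.13 or 1/(0.427 + 0.573 × 1.2) = 0.90. The documents give neither size nor direction.

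**8. Price of weekday-only controls.** √(1/135 + 1/93.6) / √(1/135 + 1/219) = 0.1345/0.1094 = 1.23, a 23% larger standard error.

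**The case against.** **Adjustment misses the main threat.** Evening and weekend care is tied to group, and step 6 shows that regression leaves it in place. This stands. The model is proposed for case mix only, and the plan should say so.

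**Case mix may not vary with the clock.** Nobody chooses when a culture turns positive, and no passage shows that patients differ by hour. This also stands: the imbalances in step 5 are assumed. A reader might infer that the comparison is known to be biased, or that chance imbalance alone would inflate the error rate. The documents do not support the first. The second is wrong, because chance imbalance is already inside the nominal 5%: with equal prevalence in both groups, the unadjusted test rejects in 4.9-5.0% of simulated trials. The higher rates need a systematic difference.

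**The bias is small beside the expected effect.** The protocol expects a fall from 90 h to 30 h, a hazard ratio near 3 if times are exponential. Against that, 1.07-1.14 is minor. But the 24/7 recommendation depends on significance, not on an effect of that size.

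**A weekday contrast seems to be planned.** A reader might infer that the SAP has none outside the Gram-negative tables. The header near Table 3A suggests otherwise, so intervention versus weekday controls is probably intended more widely. It appears unadjusted, and the sensitivity analysis as worded is still a comparison among controls.

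**Table 3 may carry a method.** It may. One might infer that the SAP has no adjusted or formal test of the primary outcome at all; the readable text cannot establish that.

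**Conclusion.** The point holds in limited form, and the sponsor should act on it. The main concurrent comparison is non-randomised, the readable SAP names no adjusted method for it, and the protocol and SAP disagree on who the concurrent controls are. The group sizes indicate that weekend patients are in the 219. They make up about 57% of control time, or 51% on the seven-day reading of the overnight rule. Both figures assume uniform positivity and are approximate because an unknown share of the 27 deviation controls may have arisen in intervention hours.

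The size and direction of any bias are unknown. The figures 1.07 and 1.14, with 7-9% and 12-20% false positives, illustrate assumed systematic imbalances of 10 and 20 points. They are not estimates for this trial. Nor do the documents show that weekend care was worse or better.

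**What to change.** 1. **Add an adjusted model.** Analyse time to optimal therapy, intervention versus concurrent controls, by a censored time-to-event regression. A cause-specific Cox model fits the SAP's censoring at death. Check proportional hazards and show the unadjusted Kaplan-Meier result beside it. Use the group as allocated by clock time, with the SAP's receipt-based grouping alongside. Adjust for items fixed at or before positivity: age, antecedent conditions, immunocompromise, and unit (NICU or other) and central line as they stood at the culture. Leave out the ICU-stay item, which may follow the culture.

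2. **Reconcile protocol section IV.C.b with the SAP's Patient Group definitions and name one primary concurrent contrast.** If the control windows are pooled, make the sensitivity analysis intervention versus Monday-to-Thursday controls from the same adjusted model. If weekday-only, state the 23% cost in standard error.

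3. **State the limit.** Adjustment addresses case mix and cannot separate the panel from evening or weekend care. Section IV.D should not call the allocation randomised.

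**Cost.** One model and some SAP wording. The covariates are already listed in Table 1A and the NICU split in Tables 3A and 3B; the status of line and unit at the time of culture needs confirming. At the historical 37%, 354 × 0.37 ≈ 131 events: 13 per parameter with age in six groups (10 parameters), or 22 with one continuous age term (6 parameters). Weekday-only gives 229 × 0.37 ≈ 85 events, or 8.5 and 14 per parameter, so a single age term is safer there. The 37% may not apply exactly to a 14-day window.
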